#### 7.1.3. COMBO 450 administration instructions

Encorafenib and binimetinib will be administered orally on a daily schedule as a flat fixed dose (not by body weight or body surface area).

Patients will be supplied during the control visit with enough number of tablets and/or capsules for all doses to be taken prior to the next scheduled visit. In addition, patients will be provided a dosing diary and should document in this diary each prescribed dose, and whether it was taken or not.

If a patient vomits at any time after dosing, the dose of study drug should not be re-administered.

Doses of binimetinib that are omitted for any reason should not be made up later if it is less than 6 hours until the next dose is due. Doses of encorafenib that are omitted any reason can be taken up to 12 hours prior to the next dose.

Patients must avoid consumption of grapefruit or grapefruit juice during the entire study and preferably 7 days before the first dose of study medications, due to potential CYP3A4 interaction with the study medications. Orange juice is allowed. Complete dosing instructions will be provided to study patients and will include the minimum times between doses and instructions for missed doses. Patients will also be instructed not to chew, crush, or dissolve tablets and/or capsules of study drugs. The investigator or responsible site personnel should instruct the patient to take the study drugs as per protocol (Sponsor compliance). All dosages prescribed and dispensed to the patient and all dose changes and all missed doses during the study must be recorded on the eCRF. Drug accountability must be performed on a regular basis. Patients will be instructed to return unused study drugs to the site at the end of each cycle. The site personnel will ensure that

the appropriate dose of each study drug is administered at each visit and will provide the patient with the correct number of drugs for subsequent dosing.

Patients should be instructed to take with a large glass of water (~250 ml) daily in the morning at approximately the same time every day the Combination of 450 mg of encorafenib and 45 mg of binimetinib (Combo 450) together. Twelve hours later, patients should take again 45 mg of binimetinib with a large glass of water (~250 ml). In total, patients should take 90 mg of binimetinib every day, if the dose has not been modified. All dose administrations may be taken with or without food, but the same method should be used consistently throughout the study. Despite this, the concomitant administration of encorafenib with grapefruit juice should be avoided.

The prescribed doses for binimetinib should be taken twice daily, approximately 12 hours apart. On visit days when the patient is scheduled to be at the clinic, patients will take encorafenib and binimetinib (as applicable) in the clinic under the supervision of the investigator or designee on the morning. On the evening of the visit day patients will take binimetinib (as applicable) at home. On all other days, patients will take encorafenib and binimetinib (as applicable) at home. If a patient temporarily interrupts treatment with binimetinib, the patient may continue treatment with encorafenib as monotherapy at a maximum dose of 300 mg QD. If binimetinib is permanently discontinued, encorafenib should be discontinued. If a patient permanently discontinues treatment with encorafenib, the patient must discontinue treatment with binimetinib, complete the end of treatment visit and continue to be followed until disease progression.

## 7.1.4. Radiation therapy 

## 7.1.4.1 Whole Brain Radiation Therapy

- 1. Total Dose:
  - The whole brain planning target volume (PTV) will receive 30 Gy in 10 fractions.
  - Treatment will be delivered once daily, 5 fractions per week, over 2 to 2.5 weeks.
  - 2. Immobilization, Simulation, Localization:
    - Patients will be treated in the supine position using an adequate immobilization (aquaplast mask).
    - A treatment-planning CT scan of the whole head region must be acquired with the
      patient in the same position and immobilization device as for treatment. Axial slice
      thickness not exceeding 3-5 mm will be required. Contrast IV and MRI-CT fusion are
      not necessary.
  - 3. Target volumes:
    - It is not necessary to define the Gross Tumour Volume (GTV).
    - The Clinical Target Volume (CTV) is defined as the whole brain parenchyma to C1 (if no posterior fossa metastasis) or C2 (if MRI evidence of posterior fossa metastasis).
    - The PTV is defined as the CTV + 0.5 cm with clip at patient surface.
  - 4. Treatment Planning:
    - Treatments must be delivered with 3-D planning through parallel opposed fields that cover the entire cranial contents (also it is allowed static or dynamic intensity modulation).
    - All portals will be treated daily.
    - Treatment will be delivered using megavoltage machines with photon beams ranging from 4 to 8 MV. Electron, particle, or implant therapy is not permissible.

# 5. Dose Specification:

- Doses will be specified at the central axis at midplane on the brain.
   90% of the whole brain PTV must be covered by the prescription dose.
- Maximum dose to 2% of the PTV (D2%) 37.5 Gy, and minimum dose to 98% of the PTV (D98%) 25 Gy.
- If treatment is delivered with Helical Tomotherapy 96% of the whole brain PTV must be covered by the prescription dose. Max dose 30 Gy, 30 Gy to >=96%.
- If LINAC-based IMRT is delivered, 92% of the whole brain PTV must be covered by the prescription dose. Max Dose 34 Gy. Min Dose: 27,6 Gy.

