#### 6. Critical Structures:

- The lenses, orbits, optic nerves, optic chiasm and brain will be contoured.
- Hippocampus protection is allowed in patients who do not present any nearby lesion, enabling the possibility of protecting said area.
- Minimize the dose to the lens and orbits. Dose to any point within the optic nerves or optic chiasm cannot exceed 37.5 Gy.
- If treatment is delivery with Helical Tomotherapy Eyes: Max Dose 8 Gy, 5 Gy <=20%. Lenses: Max Dose 3 Gy.
- If LINAC-based IMRT Involving Static Gantry Angles: Eyes: Max Dose 7 Gy, 5 Gy <=20%. Lenses: Max Dose 5 Gy.

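### For helical tomotherapy, the whole-brain maximum dose equals the prescription dose that must cover at least 96% of the target, leaving no headroom for any dose spread

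*Combined protocol and SAP*

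**What the plan says.** All the text is in protocol section 7.1.4.1 (Whole Brain Radiation Therapy).

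- **Prescription (item 1):** "The whole brain planning target volume (PTV) will receive 30 Gy in 10 fractions".
- **Target (item 3):** "The Clinical Target Volume (CTV) is defined as the whole brain parenchyma to C1" (or C2 with posterior fossa disease), and "The PTV is defined as the CTV + 0.5 cm with clip at patient surface". No part of the brain is taken out of the target.
- **General limits (item 5):** coverage of 90% of the PTV at the prescription dose, then "Maximum dose to 2% of the PTV (D2%) 37.5 Gy, and minimum dose to 98% of the PTV (D98%) 25 Gy".
- **Helical tomotherapy (item 5):** coverage of 96% of the PTV at the prescription dose, then "Max dose 30 Gy, 30 Gy to >=96" (the last figure is a percentage). No minimum dose is given.
- **LINAC-based IMRT (item 5):** coverage of 92%, then "Max Dose 34 Gy. Min Dose: 27,6 Gy".
- **Hippocampus (item 6):** "Hippocampus protection is allowed in patients who do not present any nearby lesion". Item 6 sets no hippocampal dose limit, does not include the hippocampus among the structures to contour, and does not say whether a protected hippocampus still counts toward PTV coverage or minimum dose.

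**The concern.** A coverage rule is a floor on dose over most of the target, and a maximum is a ceiling. For tomotherapy the floor and the ceiling are the same number. A planner whose dose varies at all within the covered volume must miss one of the two lines, and the protocol does not say which one gives way.

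The hippocampal permission raises a related question for LINAC-based IMRT: how far can a region be spared if it lies inside a target that has its own minimum?

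Three things are at stake:

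- **Treatment delivery.** Sites may resolve the conflict in different ways.
- **Deviations.** Section 7.1.4.2 grades its radiosurgery dose checks as per protocol, acceptable or unacceptable. Section 7.1.4.1 has no such grading, so a missed whole-brain limit has no stated tolerance.
- **Safety description.** Toxicity after local treatment is a secondary objective (section 4.2), and the first three irradiated patients form a safety run-in (section 5.3). The SAP radiotherapy tables (Tables 45 and 46) record whole-brain treatment only as given or not given, so they cannot show how a planner resolved the conflict.

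**Working it through.** There is no sample size, power or error rate to reproduce here. The check treats the limits as inequalities against the 30 Gy prescription. All inputs are from section 7.1.4.1, items 1, 3, 5 and 6.

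**1. Tomotherapy.** Let D be the dose at a point in the PTV.

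- Coverage: D ≥ 30 Gy in at least 96% of the PTV.
- Maximum, read as a point maximum in the PTV: D ≤ 30 Gy everywhere.
- Together: 30 ≤ D ≤ 30, so D = 30.0 Gy in at least 96% of the PTV. Headroom is 30 − 30 = 0 Gy.

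Reading the maximum as a near-maximum helps little. If it means D2% ≤ 30 Gy, at most 2% of the PTV may exceed 30 Gy, so at least 96% − 2% = 94% must still receive exactly 30.0 Gy. The conflict would disappear only if the maximum applied to some volume outside the PTV. The PTV is the only volume named in that bullet, and the eye and lens limits are given separately in item 6.

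**2. Comparison with the other limits in item 5.**

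| Rule | Coverage at 30 Gy | Upper limit | Upper limit ÷ 30 | Headroom |
|---|---|---|---|---|
| General | 90% | D2% 37.5 Gy | 125% | 7.5 Gy |
| LINAC-based IMRT | 92% | maximum 34 Gy | 113.3% | 4.0 Gy |
| Helical tomotherapy | 96% | maximum 30 Gy | 100% | 0 Gy |

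The 37.5 Gy figure is a general near-maximum with no technique named, so it is not the same kind of limit as the other two. The table shows only that the strictest coverage is paired with no headroom.

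**3. Hippocampus.** By item 3 it lies inside the CTV and so inside the PTV.

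- LINAC-based IMRT, reading the 27.6 Gy minimum as applying to the PTV: the largest reduction is 30 − 27.6 = 2.4 Gy, and 2.4 ÷ 30 = 8%.
- Tomotherapy: no minimum is stated, and 100% − 96% = 4% of the PTV may fall below 30 Gy.
- General rule: 100% − 90% = 10% may fall below 30 Gy, and 100% − 98% = 2% below 25 Gy.

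The documents do not give the size of a protected region, so whether it would fit within those shares cannot be worked out.

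**The case against.** The strongest reply is that this is one line of drafting with little reach, and much of that reply stands.

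- **A reader might infer that the tomotherapy limits are logically impossible.** They are not: a uniform 30.0 Gy in at least 96% of the PTV meets both. The difficulty is that the rule tolerates no spread, and the text does not define what the maximum is or where it applies.
- **A reader might infer that hippocampal protection contradicts the dose rules in general.** The documents do not support that. The 27.6 Gy minimum appears only in the LINAC-based IMRT bullet, protection is optional and has no numeric target, and the other rules allow some under-dosing. A specific permission can also be read as an exception to the target rule. What remains is an interaction left unstated for one technique.
- **A reader might infer that tomotherapy patients would be over-dosed, or that the toxicity results would be biased.** Nothing shows this. The documents give no dose distribution for such plans and do not say how many patients, if any, would have whole-brain tomotherapy. Item 4 makes parallel opposed fields the basic method and merely permits intensity modulation. Toxicity after local treatment is described, not tested (section 10.2), and the SAP safety tables are not split by technique.
- **The main result is untouched.** Intracranial response is measured before local treatment, and per-protocol exclusion for deviations is tied to that endpoint (section 10.5).

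None of this removes the core point: no other part of the documents reconciles the tomotherapy maximum with its coverage rule.

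**Conclusion.** The tomotherapy line is wrong as written. Its maximum is 100% of the prescription that must cover at least 96% of the PTV, so headroom is zero. This holds whatever spread a real plan has, and it needs no assumption about the shape of the dose distribution. It does assume that the maximum applies to the PTV. Under a near-maximum reading, at least 94% of the PTV must still be uniform.

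The hippocampal point is secondary and confined to LINAC-based IMRT: sparing is capped at 2.4 Gy (8%) unless the protected region is exempt from the minimum, and the text is silent on that. It is a gap to close rather than a contradiction.

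The consequence is limited to treatment delivery, the classification of radiotherapy deviations, and the descriptive toxicity after local treatment. Sample size, primary endpoint and analysis populations are unaffected.

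**What to change.** The trial's radiotherapy coordinators should reconcile items 1, 3, 5 and 6 of section 7.1.4.1 and state:

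1. how the tomotherapy maximum and its coverage rule are to be met together;
2. whether the maximum is a point dose or a near-maximum, and to which volume it applies;
3. whether a protected hippocampus counts toward PTV coverage and minimum dose, in particular under LINAC-based IMRT.

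Which values are right is for the coordinators to decide; none is proposed here.

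The cost is a few lines of wording. A per-patient record of which limit was missed is not recommended: item 7 of the section asks only for images verifying the isocentre, so such a record would need dose-volume data that this section does not require. SAP section 3.5 already refers to database closure with four patients still on treatment. The clarification may therefore change few or no plans and serve mainly to settle how delivered whole-brain plans are judged against the protocol.

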#### 6. Critical Structures:

- The lenses, orbits, optic nerves, optic chiasm and brain will be contoured.
- Hippocampus protection is allowed in patients who do not present any nearby lesion, enabling the possibility of protecting said area.
- Minimize the dose to the lens and orbits. Dose to any point within the optic nerves or optic chiasm cannot exceed 37.5 Gy.
- If treatment is delivery with Helical Tomotherapy Eyes: Max Dose 8 Gy, 5 Gy <=20%. Lenses: Max Dose 3 Gy.
- If LINAC-based IMRT Involving Static Gantry Angles: Eyes: Max Dose 7 Gy, 5 Gy <=20%. Lenses: Max Dose 5 Gy.

#### 7. Documentation:

 Verification of orthogonal films or portal images that localize the isocenter placement must be obtained.

#### 7.1.4.2. Radiosurgery/Stereotactic radiosurgery

- 1. All participating institutions must use approved stereotactic localization procedures for imaging and treatment delivery.
- 2. Devices: Gamma Knife or Accelerator Linac-Based Systems (IMRT, Rapid Arc, VMAT), Cyberknife, or Tomotherapy Hi-Art system.
- 3. Total Dose:
  - a. Dose selection must be based on previously published Radiation Therapy Oncology Group (RTOG) data, with dose modification left up to the treating physician. The total dose will depend on the size of the metastatic lesion(s) and proximity to critical structures.
  - b. Suggested doses are as follows: 1 fraction x 15-25 Gy; 3 fractions x 9-11 Gy; 5 fractions x 6-7 Gy; or 6 fractions x 5-6 Gy.
  - c. For GTV > 20 mm hypofractionated stereotactic radiotherapy could be prefered.
  - d. Treatment will be delivered once daily, alternate-day, 3 fractions per week.
- 4. Immobilization, Simulation, Localization:
  - a. Patients will be treated in the supine position using an adequate immobilization facemask/stereotactic frame.
  - b. A treatment-planning CT scan of the whole head region must be acquired with the patient in the same position and immobilization device as for treatment. Axial slice thickness not exceeding 2-3 mm will be required to define gross tumour volumes.
  - c. Administration IV contrast increases the diagnostic accuracy of CT.

- d. The MRI planning and treatment-planning CT should be fused.
- 5. Target volumes:
  - a. GTV will be delineated on axial T1-weighted gadolinium-enhanced MRI. Areas of edema will not be considered part of the target volume.
  - b. PTV will be defined as expanding GTV 1-2 mm.
- 6. Treatment Planning:
  - a. Treatments must be delivered with Intensity-Modulated RT. Acceptable IMRT modalities include helical tomotherapy or LINAC-based IMRT involving static gantry angles or volumetric arc therapy (VMAT). It is also possible to use Gamma Knife.
- 7. Dose Specification:
  - a. The Dose will be prescribed to the isodose surface (50-90% [maximum = 100%]), which encompasses the target, to ensure at least 95% coverage of the PTV with the prescription dose. The 100% (maximum) dose and minimum dose will be recorded for each patient.
  - b. Three isodose lines should be submitted: the prescription isodose line, 90% of the prescription isodose line (not 90% of total dose) and 80% of the prescription isodose line.
    - Acceptable variation: 80% isodose line covers the target
    - Unacceptable deviation: 80% isodose line does not cover target
  - c. Dose Homogeneity QA: The ratio of the maximum dose to the prescribed dose (MD/PD) will be:
    - Per protocol if <2
    - Acceptable variation if >2 but <2.5
    - Unacceptable deviation if >2.5
  - d. Dose Conformity QA: The ratio of prescription isodose volume to the target volume (PI/TV) is:
    - Per protocol if between 1.0 and 2.0
    - Acceptable variation if >0.9 but <1.0 or >2.0 but <3.5

    - Unacceptable deviation if >3.5
- 8. Critical Structures:
  - a. The lenses, orbits, optic nerves, optic chiasm and brain, will be contoured.
  - b. There are no clear dose limits established for organs at risk for SR or HBRT. Gerard et al. has just published a recent compilation about dose-constraints.
- 9. Documentation:
  - a. For all forms of dose delivery, immediately before treatment, images that localize the isocenter placement shall be obtained, with appropriate adjustment to ensure a translational position deviation less than 1 mm in any direction and minimal rotational deviation.

# 7.2. Dose modifications

Patients will be monitored for adverse events at each visit with the NCI CTCAE version 4.03 used for all grading. If a patient develops a toxicity, the dose may be adjusted as outlined in Table 8-9 and Table 10, which include criteria for interruption and re-initiation of encorafenib and binimetinib. All dose modifications should be based on the worst preceding toxicity (CTCAE version 4.03). All dosing interruptions and changes must be recorded on the Dosage Administration Record at eCRF.

Eye disorders should be graded according to CTCAE version 4.03 as described below in Table 3.

Table 3. CTCAE grading for eye disorders

Grade	Description		
1	Asymptomatic or mild symptoms; clinical or diagnostic observations only; intervention not indicated; no change in vision		
2	Moderate; minimal, local or non-invasive intervention indicated; limiting instrumental ADL; best corrected visual acuity 20/40 and better or 3 lines or less decreased vision from known baseline		
3	Severe or medically significant but not immediately sight threatening; limiting self-care ADL; decrease in visual acuity (best corrected visual acuity worse than 20/40 or more than 3 lines of decreased vision from known baseline, up to 20/200)		
4	Sight-threatening consequences; urgent intervention indicated; best corrected visual acuity of 20/200 or worse in the affected eye		
ADL = Activities of Daily Living			

Retinal detachment should be graded according to the CTCAE version 4.03 as described below in Table 4.

Table 4. CTCAE grading for retinal detachment

Grade	Description	
1	-	
2	Exudative and visual acuity 20/40 or better	
3	Rhegmatogenous or exudative detachment; operative intervention indicated; decline in vision (worse than 20/40 but better than 20/200	
4	Blindness (20/200 or worse) in the affected eye	
Definition: A disorder characterized by the separation of the inner retina layers from the underlying pigment epithelium.		

Uveitis should be graded according to the CTCAE version 4.03 as described below in Table 5

**Table 5. CTCAE grading for uveitis** 

Grade	Description	
1	Anterior uveitis with trace cells	
2	Anterior uveitis with 1+ or 2+ cells	
3	Anterior uveitis with 3+ or greater cells; intermediate posterior or panuveitis	
4	4 Best corrected visual acuity of 20/200 or worse in the affected eye	
Definition: A disorder characterized by inflammation to the uvea of the eye.		

Palmar-plantar erythrodysesthesia syndrome should be graded according to the CTCAE version 4.03 as described below in Table 6.

Table 6. CTCAE grading for Palmar-plantar erythrodysesthesia syndrome

Grade	Description		
1	Minimal skin changes or dermatitis (e.g., erythema, edema, or hyperkeratosis) without pain		
2	Skin changes (e.g., peeling, blisters, bleeding, fissures, edema, or hyperkeratosis) with pain; limiting instrumental ADL		
3	Severe skin changes (e.g., peeling, blisters, bleeding, fissures, edema, or hyperkeratosis) with pain; limiting self-care ADL		
4	-		

Definition: A disorder characterized by redness, marked discomfort, swelling, and tingling in the palms of the hands or the soles of the feet. Also known as Hand-Foot Syndrome.

Diarrhea should be graded according to CTCAE version 4.03 as described below in Table 7.

**Table 7. CTCAE grading for Diarrhea** 

Grade	Description	
1	Increase of <4 stools per day over baseline; mild increase in ostomy output compared to baseline	
2	Increase of 4 - 6 stools per day over baseline; moderate increase in ostomy output compared to baseline; limiting instrumental ADL	
3	Increase of >=7 stools per day over baseline; hospitalization indicated; severe increase in ostomy output compared to baseline; limiting self-care ADL	
4	Life-threatening consequences; urgent intervention indicated	
5	Death	
Definition: A disorder characterized by an increase in frequency and/or loose or watery bowel movements.		

# 7.2.1. Dose modification and dose delay for encorafenib (as monotherapy) and combination (encorafenib and binimetinib)

For patients who do not tolerate encorafenib and/or binimetinib initial dosing schedule, dose adjustment is permitted to allow the patient to continue study drug (see Table 8 for encorafenib and Table 9 for binimetinib).

A dose reduction below 100 mg QD for encorafenib and below 30 mg BID for binimetinib is not allowed. Dose interruptions of more than 28 consecutive days are not allowed unless approved by the Sponsor

Table 8. Dose reduction for encorafenib

Dose reduction based on the highest AE grade			
Dose level	Encorafenib*		
0 (starting dose)	450 mg QD (6 capsules of 75 mg)		
-1 (monotherapy dose)	300 mg QD** (4 capsules of 75 mg)		
-2	200 mg QD (2 capsules of 75 mg and 1 capsule of 50 mg)		
-3	100 mg QD*** (2 capsules of 50 mg)		

\*If binimetinib is permanently discontinued, encorafenib should be discontinued

Table 9. Dose reduction for binimetinib

Dose reduction based on the highest AE grade			
Dose level Binimetinib			
0 (starting dose) 45 mg BID (3 pills of 15 mg)			
-1 30 mg BID* (2 pills of 15 mg)			
*Dose reduction below 30 mg is not allowed			

Doses of binimetinib that are omitted for any reason should not be made up later if it is less than 6 hours until the next dose is due. Doses of encorafenib that are omitted for any reason can be taken up to 12 hours prior to the next dose. For both encorafenib and binimetinib, when the toxicity that resulted in a dose reduction improves to Grade 1 or less, the dose should be re-escalated at the investigators discretion provided there are no other concomitant toxicities.

If binimetinib is dose reduced due to left ventricular dysfunction, prolonged QTcF > 500 msec or any grade 4 toxicity related to the drug, no dose re-escalation is allowed. If encorafenib is dose reduced due to prolonged QTcF > 500 msec or any grade 4 toxicity related to the drug, no dose re-escalation is allowed. Dose reduction/interruption/discontinuation decisions should be based on the CTCAE grade of the toxicity and the guidelines provided below (Table 8). In general, doses

\*\*The maximum dose of encorafenib if it is administered as monotherapy while binimetinib is temporarily interrupted

\*\*\*Dose reduction below 100 mg is not allowed

should not be reduced or interrupted for Grade 1 toxicities, but treatment to control symptoms should be provided as appropriate. All AEs should be followed weekly or as clinically appropriate until stabilization or resolution.

If a patient temporarily interrupts treatment with binimetinib, the patient must continue treatment reducing encorafenib at dose of 300 mg QD, if patient was receiving 450 mg QD of encorafenib in combination with binimetinib (see Table 8 for encorafenib dose reductions). However, if a patient discontinues treatment with encorafenib, they must discontinue treatment with binimetinib, complete the end of treatment visit and continue to be followed until disease progression. Please refer to table 10 for dose adjustment recommendations for encorafenib and/or binimetinib induced toxicities.

Table 10. Encorafenib and binimetinib – Recommended dose modifications associated with treatment-related adverse events

Worst toxicity CTCAE v 4.03 Grade (unless otherwise specified)	Dose adjustments of both drugs	
Cutaneous reactions	Encorafenib	Binimetinib
Grade 2	Encorafenib and binimetinib should be maintained.  If rash worsens or does not improve within 2 weeks with treatment, encorafenib and binimetinib should be withheld until being Grade 0 or 1 toxicity. Then:  If it is the first occurrence of Grade 2, both drugs can be resumed at the same dose.  If it is a recurrent Grade 2 toxicity, both drugs should be resumed at a reduced dose.	
Grade 3	
 
Encorafenib and binimetinib should be withheld until improvement to Grade 0 or 1 toxicity. Then:
 
If it is the first occurrence of Grade 3, both drugs can be resumed at the same dose.
 
If it is a recurrent Grade 3 toxicity, both drugs should be resumed at a reduced dose.
 
	
Grade 4	Encorafenib and binimetinib should be permanently discontinued.	
Squamous Cell Carcinoma (SCC), Keratoacanthoma (KA) or any other suspicious skin lesion	Encorafenib	Binimetinib
Grade 3-4	Encorafenib and binimetinib should be maintained at same dose and local treatment of lesion (e.g. new primary melanoma) should be done based upon institutional practice.	
Palmar-plantar erythrodysaesthesia syndrome (PPES)	Encorafenib	Binimetinib

Grade 2		Encorafenib and binimetinib should be maintained and supportive measures such as topical therapy should be instituted.  If not improvement despite supportive therapy within 2 weeks, encorafenib and binimetinib should be withheld until improvement to Grade 0 or 1 toxicity. Then, treatment should be resumed at the same dose level or at a reduced dose of encorafenib.	
Grade 3		as topical therapy should be instit weekly until improvement to Grad	d be withheld, supportive measures such cuted, and patients should be reassessed e 0 or 1 toxicity. Then, treatment should el or at a reduced dose of encorafenib.
Liver laboratory abnormalities		Encorafenib	Binimetinib
Grade 2	Encorafenib and binimetinib should be maintained.  If no improvement within 2 weeks, binimetinib should improved to Grade 0 or 1 or to baseline levels. At same should be reduced to 300mg QD if the patient was reencorafenib QD with binimetinib.  If no improvement within 4 weeks, encorafenib should improved to Grade 0 or 1 or to baseline levels.  Then, both drugs should be resumed at the same dose.		cs, binimetinib should be withheld until seline levels. At same time, encorafenib of if the patient was receiving 450mg of cs, encorafenib should be withheld until seline levels.
Grade 3, first occurrence  Grade 3,	AST or ALT >5x ULN + blood bilirubin >2x ULN	Encorafenib and binimetinib should be withheld for up to 4 weeks.     If toxicity improves to Grade 0 or 1 or to baseline levels, both drugs should be resumed at a reduced dose.     If toxicity doesn't improve both drugs should be permanently discontinued.  It should be considered to permanently discontinue encorafenib and	
Grade 4, first occurrence	AST or ALT >20x ULN	
 
binimetinib.
 
Encorafenib and binimetinib should be withheld for up to 4 weeks.
 
If toxicity improves to Grade 0 or 1 or to baseline levels, both drugs should be resumed at a reduced dose level.
 
If toxicity doesn't improve both drugs should be permanently discontinued.
 
Or, encorafenib and binimetinib should be permanently discontinued.
 
	
Grade 4, recurrent		Encorafenib and binimetinib should be permanently discontinued.	
QTc prolongation		Encorafenib	Binimetinib
